Appendix C. Pregnancy and Lactation Notification Worksheets

AMGEN® Pregnancy Notification Worksheet

Fax Completed Form to the Country-respective Safety Fax Line

SELECT OR TYPE IN A FAX#

1. Case Administrative Information				
Protocol/Study Number: 20120227				
Study Design:  Interventional  Observational (If Observational:  Prospective  Retrospective)				
2. Contact Information				
Investigator Name			Site #	
Phone (____)	Fax (____)	Email _____		
Institution _____				
Address _____				
3. Subject Information				
Subject ID #	Subject Gender:  Female  Male Subject DOB: mm  / dd  / yyyy 			
4. Amgen Product Exposure				
Amgen Product	Dose at time of conception	Frequency	Route	Start Date
				mm  / dd  / yyyy 
Was the Amgen product (or study drug) discontinued?  Yes  No				
If yes, provide product (or study drug) stop date: mm  / dd  / yyyy 				
Did the subject withdraw from the study?  Yes  No				
5. Pregnancy Information				
Pregnant female's LMP	mm  / dd  / yyyy 	 Unknown		
Estimated date of delivery	mm  / dd  / yyyy 	 Unknown  N/A		
If N/A, date of termination (actual or planned) mm  / dd  / yyyy 				
Has the pregnant female already delivered?  Yes  No  Unknown  N/A				
If yes, provide date of delivery: mm  / dd  / yyyy 				
Was the infant healthy?  Yes  No  Unknown  N/A				
If any Adverse Event was experienced by the infant, provide brief details: 				

Form Completed by:	
Print Name:	Title: _____
Signature: 	Date: _____

Approved

AMGEN® Lactation Notification Worksheet

Fax Completed Form to the Country-respective Safety Fax Line

SELECT OR TYPE IN A FAX# **1. Case Administrative Information**Protocol/Study Number: 20120227Study Design: Interventional Observational (If Observational: Prospective Retrospective)**2. Contact Information**

Investigator Name _____ Site # _____

Phone (_____) _____ Fax (_____) _____ Email _____

Institution _____

Address _____

3. Subject Information

Subject ID # _____ Subject Date of Birth: mm_____/dd_____/yyyy_____

4. Amgen Product Exposure

Amgen Product	Dose at time of breast feeding	Frequency	Route	Start Date
				mm_____/dd_____/yyyy_____

Was the Amgen product (or study drug) discontinued? Yes No

If yes, provide product (or study drug) stop date: mm_____/dd_____/yyyy_____

Did the subject withdraw from the study? Yes No**5. Breast Feeding Information**Did the mother breastfeed or provide the infant with pumped breast milk while actively taking an Amgen product? Yes No

If No, provide stop date: mm_____/dd_____/yyyy_____

Infant date of birth: mm_____/dd_____/yyyy_____

Infant gender: Female MaleIs the infant healthy? Yes No Unknown N/A

If any Adverse Event was experienced by the mother or the infant, provide brief details:

Form Completed by:

Print Name: _____

Title: _____

Signature: _____

Date: _____

Approved

Appendix D. Excluded Medications and Foods

CYP3A4 Inducers	CYP3A4 Inhibitors
Carbamazepine	Amprenavir
Dexamethasone	Cobicistat
Efavirenz	Cyclosporine
Etravirine	Clarithromycin
Nevirapine	Delavirdine
Phenobarbital	Erythromycin
Phenytoin	Grapefruit juice
Rifabutin	Indinavir
Rifampicin	Itraconazole
St. John's wort	Nelfinavir
	Ritonavir
	Saquinavir
	Telaprevir
	Verapamil
	Voriconazole

Approved

Table of Abbreviations

Abbreviation or Term	Definition/Explanation
ACE	angiotensin-converting enzyme
AE	adverse event
ALP	alkaline phosphatase
ALT	alanine aminotransferase
ARB	angiotensin receptor blocker
AST	aspartate aminotransferase
AUC	area under the curve
AUC ₁₂	area under the concentration-time curve for a 12 hour-dosing interval
AUC _t	area under the concentration-time curve calculated by linear trapezoidal method
ANCOVA	analysis of covariance
BID	twice daily
BMI	body mass index
BNP	brain-type natriuretic peptide
Bpm	beats per minute
C _{2h}	observed plasma concentration 2 hours after morning investigation product administration
CAS	completer analysis set
CDM	clinical data management
CEC	clinical events committee
CHF	chronic heart failure
CI	confidence interval
CK-MB	creatinine kinase MB fraction
C _{max}	maximum observed plasma concentration
CPMS	Clinical Pharmacology, Modeling and Simulation
C _{predose}	plasma concentration prior to the investigational product administration
CSR	clinical study report
CTCAE	common terminology criteria for adverse events; common toxicity criteria for adverse events
DLRM	dose level review meeting
DMC	data monitoring committee
DQR	data quality review
ECG	electrocardiogram
eCRF	electronic case report form

Abbreviation or Term	Definition/Explanation
eGFR	estimated glomerular filtration rate; eGFR will be calculated by the central laboratory and provided to the investigator
EOI	events of interest
EOS	end of study (for individual subject)
E-R	exposure-response
FAS	full analysis set
HF	heart failure
HR	heart rate
IBG	independent biostatistical group
IP	investigational product
IPD	important protocol deviation
IVRS	interactive voice response system
LLOQ	lower limit of quantification
LVEDD	left ventricular end-diastolic diameter
LVEDV	left ventricular end-diastolic volume
LVEF	left ventricular ejection fraction
LVESD	left ventricular end-systolic diameter
LVESV	left ventricular end-systolic volume
LVFS	left ventricular fractional shortening
MedDRA	medical dictionary for regulatory activities
MI	myocardial infarction
MR	modified-release
NYHA	New York heart association
NT-proBNP	n-terminal proBNP (brain natriuretic peptide)
PK/PD	pharmacokinetic/pharmacodynamic
PKAS	pharmacokinetic analysis set
PKS	Pharsight Knowledgebase Server
PR interval	PR interval is measured from the beginning of the P wave to the beginning of the QRS complex in the heart's electrical cycle as measured by ECG
PT	prothrombin time
QRS complex	interval between the Q wave and the S wave in the heart's electrical cycle as measured by ECG; represents the time it takes for the depolarization of the ventricles
QT interval	measure of the time between the start of the Q wave and the end of the T wave in the heart's electrical cycle as measured by ECG
QTcB interval	QT interval corrected for heart rate using Bazett's formula

Abbreviation or Term	Definition/Explanation
QTcF interval	QT interval corrected for heart rate using Fridericia's formula
RR interval	interval between successive Rs where R is a point corresponding to the peak of the QRS complex as measured by ECG
SAE	serious adverse event
SAP	statistical analysis plan
SD	standard deviation
SET	systolic ejection time
SV	stroke volume
$t_{1/2}$	terminal half-life
t_{\max}	time to C_{\max}
ULN	upper limit of normal
URL	upper reference limit

Also refer to the protocol for more abbreviations on clinical terms.

1. Introduction

The purpose of this Statistical Analysis Plan (SAP) is to provide details of the statistical analyses that have been outlined within the protocol for AMG 423 (Omeamtiv Mecarbil) Study 20120227, dated 23 October 2015. The scope of this plan includes the final analyses that are planned and will be executed by the Biostatistics department. The pharmacokinetics (PK) analysis will be performed by Department of Clinical Pharmacology, Modeling and Simulation (CPMS).

2. Objectives

2.1 Primary

The primary objectives of this study are (i) to evaluate the pharmacokinetics (PK) of omecamtiv mecarbil in Japanese subjects with heart failure (HF) with reduced ejection fraction and (ii) to evaluate the safety and tolerability of oral omecamtiv mecarbil.

2.2 Secondary

Secondary objective is:

- To measure changes in systolic ejection time (SET) by echocardiography following 16 weeks of treatment.

3. Study Overview

3.1 Study Design

This is a double-blind, randomized, placebo-controlled, multicenter, phase 2 study in Japanese HF subjects to evaluate 16 weeks of administration of oral MR omecamtiv mecarbil formulation at 3 dose levels (25 mg BID, 37.5 mg BID, and 50 mg BID), compared with placebo. Potential subjects will be screened to assess their eligibility to enter the study within 30 days prior to enrollment. Subjects are eligible for screening if they have chronic stable HF and reduced ejection fraction. Subjects may also be screened in the hospital setting once they have recovered and are considered clinically stable by the investigator. Subjects must be outpatients at the time of randomization.

Approximately 80 Japanese subjects with chronic stable HF with reduced ejection fraction will be randomized 1:1:1:1 to receive omecamtiv mecarbil either 25 mg BID dose (n=20), 37.5 mg BID dose (n=20), 50 mg BID dose (n=20) or placebo (n=20) on an outpatient basis. Subjects randomized to 37.5 mg BID target dose and 50 mg BID target dose will initiate administration at 25 mg BID and will be up-titrated to 37.5 mg BID or 50 mg BID respectively at the week 4 visit based on steady state concentration prior to investigational product (IP) administration ($C_{predose}$) result from week 2. Subjects who do not have a week 2 PK value in time for dose adjustment at the week 4 visit will be

up-titrated at week 8 based on the steady state C_{predose} result from week 2, if available. Subjects will be up-titrated to 37.5 mg BID or 50 mg BID at the week 4 or week 8 visits in the titration groups only if the week 2 C_{predose} is < 200 ng/mL. Subjects with a week 2 $C_{\text{predose}} \geq 200$ ng/mL (or not available at week 8) will continue at 25 mg BID for the remainder of the study. Subjects randomized to placebo or to 25 mg BID will receive the assigned IP throughout the study. IP compliance will also be monitored. PK analysis and dose assignment will be blinded to the study team. To maintain blinding, all subjects will receive new IP supply at the week 4 and week 8 visits. The study includes transthoracic echocardiographic assessments (screening, week 8, and week 16). Enrollment of subjects with atrial fibrillation/flutter at the time of screening will be limited to approximately 20% of planned enrollment. Randomization will be stratified by presence or absence of atrial fibrillation/flutter via the interactive voice response system/interactive Web response system (IVRS/IWRS).

An independent DMC will perform regular formal unblinded review of the accumulating study data. An independent CEC will adjudicate deaths, all hospitalizations, and selected nonfatal cardiovascular (CV) events (including possible MI or ischemia). The end of study (EOS) visit will be performed 4 weeks after the last dose of IP (Week 20 +3 days).

Vital signs, physical examinations, ECGs, Adverse Event/Serious Adverse Event assessments, clinical laboratory evaluations (see Table 3 in protocol), and collection of concomitant medications will be performed at screening and at specified times per the Schedule of Assessments (see Table 2 in protocol). The overall study design is described by a study schema at the end of the protocol synopsis section. Detailed study procedures are provided in Protocol Section 7. The study endpoints are defined in [Section 4.1](#).

3.2 Sample Size

The primary endpoints of this study are the omecamtiv mecarbil PK parameters. PK parameter's mean will be estimated. Assuming the SDs for C_{max} and AUC are in the range of 40 to 90, a sample size of $n= 20$ subjects in each treatment group, 19 subjects (assuming 5% subjects out of a total $n = 20$ subjects per treatment arm are excluded from PKAS) will provide a 2-sided 95% confidence interval (CI) with half width of 18 to 41. The SD estimates are from the predicted steady state PK for 25 mg and 50 mg BID doses for Matrix F1 formulation based on simulations performed using PK data following single dose from study 20090727. The table below presents CI half widths given particular SDs in this range for 19 subjects per treatment group.

PK Parameter 95% Confidence Intervals

Standard Deviation	Confidence Interval Half Width	
	N = 19	
40		18.0
50		22.5
60		27.0
70		31.5
80		36.0
90		40.5

4. Study Endpoints and Covariates

4.1 Study Endpoints

4.1.1 Primary Endpoints

- Concentrations prior to administration (C_{predose}) of omecamtiv mecarbil at weeks 2, 4, 12, and 16, and area under the curve (AUC) at week 8

4.1.2 Secondary Endpoint

- Changes from baseline in SET by echocardiography at week 16

4.1.3 Safety Endpoints

Safety endpoints are as follows:

- Subject incidence of adverse events (AEs)
- Changes from baseline in laboratory values and vital signs
- Changes from baseline in ECG

4.1.4 Exploratory Endpoints

Exploratory endpoints are as follows:

- observed values and change from baseline to assessed timepoints of stroke volume, left ventricular end-systolic diameter (LVESD) and left ventricular end-diastolic diameter (LVEDD)
- observed values and change from baseline to assessed timepoints of HR
- observed values and change from baseline to assessed timepoints of NT-proBNP
- subject incidence of supraventricular tachycardia and ventricular tachycardia arrhythmias requiring treatment from initiation of IP to EOS
- subject incidence of the following clinical outcome endpoints:
 - cardiovascular death or HF hospitalization until EOS
 - all-cause death or HF hospitalization until EOS

- all adjudicated events until EOS; events include, but may not be limited to: cardiovascular death, HF, acute myocardial infarction, myocardial ischemia, unstable angina, and resuscitated sudden death
- new onset atrial fibrillation/flutter
- all-cause death

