10.1.2 Analysis Sets

The PK analysis set (PKAS) includes all randomized subjects who have received at least one dose of omecamtiv mecarbil and have at least one evaluable omecamtiv mecarbil PK parameter (C_{max} , $C_{predose}$). This analysis set will be used for analyses of all the PK endpoints, unless significant protocol deviations have affected the data or if key dosing or sampling information are missing, in which case a modified PKAS will be used.

The full analysis set (FAS) includes all randomized subjects who have received at least one dose of IP (omecamtiv mecarbil or placebo). This set will be used for all analyses of non-PK endpoints.

The completers analysis set is a subset of the FAS and includes subjects who have completed IP administration. The completers analysis set will be used for sensitivity analyses.

Approved

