7.2 Full Analysis Set

The full analysis set (FAS) includes all randomized subjects who have received at least one dose of IP (omecamtiv mecarbil or placebo). Efficacy analyses of the secondary and exploratory endpoints will be performed on FAS. All subjects will be analyzed according to their randomized treatment assignment.

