10.7 Analyses of Exploratory Endpoints

Both continuous and categorical exploratory endpoints will be summarized descriptively by cohort, treatment group, and scheduled assessment.

Mean differences between treatment groups in SV, LVESD, LVEDD, and HR change from baseline at scheduled assessments will be estimated via repeated-measures model

including all observed values, with difference estimates and their 95% confidence intervals presented. The model will include IVRS stratification factor, baseline value, treatment group, visit and the interaction of treatment group and visit.

NT-proBNP will be summarized descriptively and analyzed in the same principle as echocardiographic parameters.

For clinical outcome endpoints specified in [Section 4.1.4](#), subject incidence rates for each treatment group will be provided.

For each subject, the first dose date of IP will be used as the starting point for all time-to-event calculation. For each qualifying event, the onset date adjudicated by CEC will be used as event onset date for time-to-event calculation. If not otherwise specified, the adjudicated events that occurred between the first dose date of IP and the end of study date will be included in the analyses of the time-to-event clinical outcome endpoints. Subjects who did not experience a qualifying event will be right censored at the end of study.

Supraventricular tachycardia and ventricular tachycardia arrhythmias will be identified from the corresponding eCRF forms. Subject incidence of supraventricular tachycardia and ventricular tachycardia arrhythmias requiring treatment from initiation of IP to end of study will be summarized for each treatment group.

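### New-onset AF/flutter incidence is set on the whole FAS, so subjects already in AF/flutter at screening (at most about 20%) dilute the absolute rates

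*SAP*

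**What the plan says.** - **Endpoint.** SAP 4.1.4 and Protocol 10.1.1.4 list "new onset atrial fibrillation/flutter" among the clinical outcomes to be reported as subject incidence. Neither document defines new onset.
- **Measure.** For the clinical outcomes, SAP 10.7 says that "subject incidence rates for each treatment group will be provided". It gives no rule for the denominator.
- **Analysis set.** SAP 7.2 states: "Efficacy analyses of the secondary and exploratory endpoints will be performed on FAS". Protocol 10.1.2 says of the FAS: "This set will be used for all analyses of non-PK endpoints". The FAS is everyone randomized and dosed at least once, and rhythm at baseline plays no part in it. Treating the endpoint as a safety outcome changes nothing, because SAP 7.3 defines the Safety Analysis Set as identical to the FAS.
- **Who is enrolled.** AF/flutter is not an exclusion criterion. SAP 3.1 says: "Enrollment of subjects with atrial fibrillation/flutter at the time of screening will be limited to approximately 20% of planned enrollment". Randomization is stratified by this factor.
- **Size.** SAP 3.1: "Approximately 80 Japanese subjects with chronic stable HF with reduced ejection fraction will be randomized 1:1:1:1", that is, 20 per arm.
- **Subgroups.** The AF/flutter subgroup analysis in SAP 7.5 applies only to the echocardiographic secondary endpoint.

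**The concern.** A subject already in AF/flutter at entry cannot ordinarily have a first episode during the trial. Such subjects can add nothing to the numerator but are counted in the denominator. The time-to-event wording in SAP 10.7 works the same way: anyone without a qualifying event is censored at end of study, so a subject with prevalent AF/flutter would contribute event-free follow-up.

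The analysis is purely descriptive, so the printed percentage is the result. For an arrhythmia outcome, a denominator that includes subjects not at risk errs towards making the event look rarer. The SAP takes account of baseline or current status elsewhere: SAP 10.8.4 drops ECG observations showing atrial fibrillation or flutter, and SAP 10.8.2 breaks troponin status down by baseline status. The omission here looks like an oversight.

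**Working it through.** The documents state no rate, count or precision for this endpoint, so there is no plan figure to reproduce. The only precision calculation (SAP 3.2) concerns PK means.

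**Inputs**
- N = 20 per arm (SAP 3.1).
- f = share of an arm with AF/flutter at screening. The ceiling is approximately 20% (SAP 3.1), or 0.20 × 80 = 16 subjects, about 4 per arm under stratified randomization. The actual share is not given, so 5% to 20% is shown.
- x = new-onset events per arm. This is an assumption; 1 to 3 is shown.

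**Formulae**
- FAS incidence = x / N
- At-risk incidence = x / [N(1 - f)]
- Ratio of FAS to at-risk incidence = 1 - f

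**Effect of f, with x = 2 assumed (FAS incidence 2/20 = 10.0%)**

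| f | At risk per arm | At-risk incidence | At-risk ÷ FAS | Relative understatement |
|---|---|---|---|---|
| 5% | 19 | 2/19 = 10.5% | 1.05 | 5% |
| 10% | 18 | 2/18 = 11.1% | 1.11 | 10% |
| 15% | 17 | 2/17 = 11.8% | 1.18 | 15% |
| 20% | 16 | 2/16 = 12.5% | 1.25 | 20% |

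**Effect of x, at the cap (f = 20%)**

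| x | FAS | At risk | Gap |
|---|---|---|---|
| 1 | 1/20 = 5.0% | 1/16 = 6.25% | 1.25 points |
| 2 | 2/20 = 10.0% | 2/16 = 12.5% | 2.5 points |
| 3 | 3/20 = 15.0% | 3/16 = 18.75% | 3.75 points |

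**Effect on arm comparisons.** Take assumed at-risk rates of 10% and 5%, with f = 20% in both arms. The FAS rates are 0.8 × 10% = 8% and 0.8 × 5% = 4%. The risk difference falls from 5 to 4 points. The risk ratio is 10/5 = 2.0 at risk and 8/4 = 2.0 on the FAS. In general the FAS risk ratio equals the at-risk ratio times (1 - f₁)/(1 - f₀), which is 1 when the arms are balanced. A one-subject imbalance (4 against 5 of 20) would give 16/15 = 1.07.

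**Against sampling error.** At x = 2 the standard error is √(0.10 × 0.90/20) = 6.7 points on the FAS and √(0.125 × 0.875/16) = 8.3 points at risk. The 2.5-point gap is less than half of either.

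**The case against.** **The plan names a set, not a table denominator.** A table shell could still print an at-risk n. That is possible, but no shell is in the documents. A programmer who follows SAP 7.2 and 10.7 as written divides by the FAS count.

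**Without a definition of new onset, it is not certain that prevalent subjects cannot have the event.** New flutter in a subject with prior fibrillation might be meant to count. This stands as a limit on the arithmetic: if recurrences were counted, the numerator would rise and the direction of the error would no longer be fixed. It also strengthens the case for a definition, since the label would then be wrong.

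**The stratum alone does not identify who is at risk.** The protocol synopsis ties it to status at screening. A subject with earlier paroxysmal AF who is in sinus rhythm at screening could sit in the absent stratum, and a recurrence could then be counted as new. This stands, and it is why the fix also uses ECG and medical history.

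**Readers can correct the figure themselves.** SAP 10.4 tabulates the stratification factor by randomized group. This helps only approximately: that table covers all randomized subjects and takes no account of AF/flutter history.

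**Nothing turns on it.** The endpoint is one exploratory item, no hypothesis is tested, and the shift is small against sampling error. This stands, and it sets the severity.

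**Conclusion.** The point holds, with low impact. Followed as written, the plan reports absolute new-onset incidence and risk differences at (1 - f) times their at-risk values. The relative understatement is at most about 20% at the enrollment cap, and 5% to 10% if 5% to 10% of subjects have AF/flutter at screening. This rests on the ordinary meaning of new onset, on all counted events arising in subjects without AF/flutter at screening, and, for the percentages shown, on assumed event counts.

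Three stronger readings are tempting, and the documents do not support them:

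- **That rates will be understated by 20%.** The 20% is a ceiling on enrollment, stated as approximate, and not an expected share.
- **That the comparison between arms is biased or a treatment signal hidden.** Stratified randomization should spread prevalent cases about evenly. The risk ratio is then essentially unchanged, and the risk difference shrinks only in proportion to the rates.
- **That the figure cannot be compared with other trials.** The documents do not say which denominators other studies use.

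The trial's primary and secondary conclusions are not affected.

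**What to change.** Add to SAP 10.7:

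1. **Definition.** New onset is a first AF/flutter event after the first dose in a subject with no prior AF/flutter.
2. **Denominator.** Compute incidence among FAS subjects who are in the AF/flutter-absent stratum, show no AF/flutter on the screening or Day 1 ECG, and have none in the recorded medical history.
3. **Display.** Print the at-risk n for each arm beside the event count. The FAS-based figure may be kept alongside, which also respects the FAS rule in Protocol 10.1.2.

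The cost is a sentence or two in the SAP. The stratum is held in the IVRS, and the schedule in Protocol 7.1 already collects the ECGs and medical history, so no new data or protocol amendment is needed. The downside is a smaller denominator (about 16 instead of 20 per arm at the cap, and fewer if some subjects have a history of AF/flutter only) and slightly wider uncertainty.
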